### **6.6.3 Management of AEs Associated with Nivolumab and Ipilimumab**

The assigned dose for nivolumab is 3 mg/kg IV q3w for the first four doses followed by 480 mg IV q4w.

The assigned dose for ipilimumab is 1 mg/kg IV q3w for a maximum of up to four doses.

Dose reductions are not allowed for nivolumab or ipilimumab. AEs associated with nivolumab and ipilimumab are managed with dose delays.

For more detailed guidance on management of non-hepatocellular AEs associated with nivolumab and ipilimumab please see [Appendix E](#). For recommendations on management of hepatocellular toxicity and dose modifications of both cabozantinib/placebo treatment and nivolumab/ipilimumab treatment, see [Section 6.6.1](#)

#### **6.6.3.1 Immune-related Adverse Events (irAEs)**

The immune-modulating properties of ICIs, such as the anti-PD-1 antibody nivolumab, and anti-CTLA-4 antibody ipilimumab are able to undermine immunologic tolerance and generate a subset of AEs (called immune related AEs or irAEs) with an autoimmune inflammatory pathomechanism. IrAEs may involve every organ or tissue (Michot et al 2016). Most irAEs occur within the first 12 weeks of exposure to ICIs but some of them may appear with a delayed onset. Diagnosis of irAEs should be based on exposure to an ICI and a reasonable immune-based mechanism of the observed AE. Whenever possible, histologic examination or other immune-based diagnostic evaluations should be used to support the diagnosis. Other etiologic causes including AEs from tumor progression should be ruled out.

The spectrum of irAEs is wide and can be general or organ-specific. Examples of general irAEs in subjects treated with ICIs such as nivolumab are fatigue, fever, and chills. Organ-specific irAEs consist of pneumonitis, colitis, hepatitis, nephritis and renal dysfunction, skin adverse reactions, encephalitis, myocarditis, and endocrinopathies (hypophysitis, adrenal insufficiency, hyperglycemia).

Early recognition and management of irAEs associated with immuno-oncology agents may mitigate severe toxicity. Medical management of irAEs focuses on suppressing the immune response with non-steroidal and steroid anti-inflammatory medication. Management algorithms have been developed and should be followed for subjects with suspected irAEs. Further information on management of nivolumab/ipilimumab-associated irAEs is provided in [Section 6.6.3.2](#) and [Appendix E](#), and can also be found in the US PI.

#### **6.6.3.2 Dose Modification Criteria for Nivolumab and Ipilimumab**

For dose modification criteria and management of AEs related to hepatotoxicity, refer to [Table 6-3](#). For other AEs categorized by SOC, refer to [Table 6-10](#). Further criteria and guidance for dose delays, resumptions and discontinuations of nivolumab and ipilimumab are provided in [Sections 6.6.3.2.1](#) and [6.6.3.2.2](#).

**Table 6-10: Adverse Event Criteria for Dose Delay, Resumption, and Discontinuation of Nivolumab and Ipilimumab**

Drug-Related AEs per CTCAE V5	Severity	Action Taken	Clarifications, Exceptions, and Resume Criteria
Gastrointestinal			
Colitis or Diarrhea	Grade 2	Delay dose.	Dosing may resume when AE resolves to baseline.
	Grade 3	Nivolumab monotherapy: Delay dose.	Dosing may resume when AE resolves to baseline.
		When administered with ipilimumab: Permanently discontinue Ipilimumab.	Nivolumab monotherapy may be resumed when AE resolves to baseline. If Grade 3 diarrhea or colitis recurs while on nivolumab monotherapy, permanently discontinue.
	Grade 4	Permanently discontinue.	-
Renal			
Serum Creatinine Increased	Grade 2 or 3	Delay dose.	Dosing may resume when AE resolves to Grade $\leq$ 1 or baseline value.
	Grade 4	Permanently discontinue.	-
Pulmonary			
Pneumonitis	Grade 2	Delay dose.	Dosing may resume after pneumonitis has resolved to $\leq$ Grade 1.
	Grade 3 or 4	Permanently discontinue.	-

CONFIDENTIAL

Protocol XL184-313 Protocol Amendment 3.0  
Page 104 of 193

Drug-Related AEs per CTCAE V5	Severity	Action Taken	Clarifications, Exceptions, and Resume Criteria
Endocrinopathy			

 
May resume treatment if drug-related endocrinopathies adequately controlled with only physiologic hormone replacement.
 
			
Adrenal Insufficiency	Grade 2 adrenal insufficiency	Delay dose.	Dosing may resume after adequately controlled with hormone replacement.
	Grade 3 or 4 adrenal insufficiency or adrenal crisis	Delay dose or permanently discontinue.	Mandatory discussion with and approval from the Medical Monitor needed prior to resuming therapy. If adrenal insufficiency resolves or is adequately controlled with physiologic hormone replacement, participant may not require discontinuation of study drug.
Hyperglycemia	Hyperglycemia requiring initiation or change in daily management (Grade 2 or 3)	Delay dose.	Dosing may resume if hyperglycemia resolves to Grade $\leq 1$ or baseline value, or is adequately controlled with glucose-controlling agents.
	Grade 4	Delay dose or permanently discontinue.	Mandatory discussion with and approval from the Medical Monitor needed prior to resuming therapy. If hyperglycemia resolves, or is adequately controlled with glucose-controlling agents, participant may not require discontinuation of study drug.
Hypophysitis or Hypopituitarism	Symptomatic Grade 1-3 that is also associated with corresponding abnormal lab and/or pituitary scan	Delay dose.	Dosing may resume if endocrinopathy resolves to be asymptomatic, or is adequately controlled with only physiologic hormone replacement.
	Grade 4	Delay dose or permanently discontinue.	Mandatory discussion with and approval from the Medical Monitor needed prior to resuming therapy. If endocrinopathy resolves or is adequately controlled with physiologic hormone replacement, participant may not require discontinuation of study drug.

CONFIDENTIAL

Drug-Related AEs per CTCAE V5	Severity	Action Taken	Clarifications, Exceptions, and Resume Criteria
Hyperthyroidism or <del>-</del> Hypothyroidism	Grade 2 or 3	Delay dose.	Dosing may resume if endocrinopathy resolves to be asymptomatic, or is adequately controlled with only physiologic hormone replacement or other medical management.
	Grade 4	Delay dose or permanently discontinue.	Mandatory discussion with and approval from the Medical Monitor needed prior to resuming therapy. If endocrinopathy resolves or is adequately controlled with physiologic hormone replacement or other medical management, participant may not require discontinuation of study drug.
Skin			
Rash	Grade 2 rash covering > 30% body surface area or Grade 3 rash	Delay dose.	Dosing may resume when rash reduces to $\leq$ 10% body surface area.
	Suspected Stevens-Johnson syndrome (SJS), toxic epidermal necrolysis (TEN) or drug reaction with eosinophilia and systemic symptoms (DRESS)	Delay dose.	Dosing may resume if SJS, TEN, or DRESS is ruled out and rash reduces to $\leq$ 10% body surface area.
	Grade 4 rash or confirmed SJS, TEN, or DRESS	Permanently discontinue.	-
Neurological			
Guillain-Barre Syndrome (GBS)	Any Grade	Permanently discontinue.	-
Myasthenia Gravis (MG)	Any Grade	Permanently discontinue.	-
Encephalitis	Any Grade encephalitis	Delay dose.	After workup for differential diagnosis, (ie, infection, tumor-related), if encephalitis is not drug related, then dosing may resume when AE resolves.
	Any Grade drug-related encephalitis	Permanently discontinue.	-

CONFIDENTIAL

Drug-Related AEs per CTCAE V5	Severity	Action Taken	Clarifications, Exceptions, and Resume Criteria
Myelitis	Any Grade myelitis	Delay dose.	After workup for differential diagnosis, (ie, infection, tumor-related), if myelitis is not drug related, then dosing may resume when AE resolves.
	Any Grade drug-related myelitis	Permanently discontinue.	-
Neurological (other than GBS, MG, encephalitis, or myelitis)	Grade 2	Delay dose.	Dosing may resume when AE resolves to baseline.
	Grade 3 or 4	Permanently discontinue.	-
Myocarditis			
Myocarditis	Symptoms induced from mild to moderate activity or exertion	Delay dose.	Dosing may resume after myocarditis has resolved.
	Severe or life threatening, with symptoms at rest or with minimal activity or exertion, and/or where intervention indicated.	Permanently discontinue.	-
Other Clinical AE			
Pancreatitis:	Grade 3 with symptoms	Delay dose.	Note: Grade 3 increased amylase or lipase without signs or symptoms of pancreatitis does not require dose delay. Dosing may resume when patient becomes asymptomatic.
Amylase or Lipase increased	Grade 4	Permanently discontinue unless an alternative etiology (such as pancreatic metastases) fully explains the findings.	-
Uveitis	Grade 2 uveitis	Delay dose.	Dosing may resume if uveitis responds to topical therapy (eye drops) and after uveitis resolves to Grade $\leq 1$ or baseline. If patient requires oral steroids for uveitis, then permanently discontinue study drug.
	Grade 3 or 4 uveitis	Permanently discontinue.	-

CONFIDENTIAL

Protocol XL184-313 Protocol Amendment 3.0  
Page 107 of 193

Drug-Related AEs per CTCAE V5	Severity	Action Taken	Clarifications, Exceptions, and Resume Criteria
Other Drug-Related AE (not listed above)	Grade 2 non-skin AE, except fatigue	Delay dose.	Dosing may resume when AE resolves to Grade $\leq 1$ or baseline value.
	Grade 3 AE - First occurrence lasting $\leq 7$ days	Delay dose.	Dosing may resume when AE resolves to Grade $\leq 1$ or baseline value.
	Grade 3 AE - First occurrence lasting $> 7$ days	Permanently discontinue.	-
	Recurrence of Grade 3 AE of any duration	Permanently discontinue.	-
	Grade 4 or Life-threatening adverse reaction	Permanently discontinue.	-
Other Lab abnormalities			
Other drug-related lab abnormality (not listed above)	Grade 3	Delay dose.	Exceptions: No delay required for Grade 3 lymphopenia. Permanent Discontinuation for Grade 3 thrombocytopenia <math>> 7</math> days or associated with bleeding.
	Grade 4	Permanently discontinue.	Exceptions: The following events do not require discontinuation of study drug: 
 
• Grade 4 neutropenia <math>\leq 7</math> days
 
• Grade 4 lymphopenia or leukopenia
 
• Grade 4 isolated electrolyte imbalances/abnormalities that are not associated with clinical sequelae and are responding to supplementation/appropriate management within 72 hours of their onset
 

Infusion Reactions (manifested by fever, chills, rigors, headache, rash, pruritus, arthralgia, hypotension, hypertension, bronchospasm, or other allergic-like reactions.)			
Hypersensitivity reaction or infusion reaction	Grade 3 or 4	Permanently discontinue.	Refer to Section 6.6.3.3 on treatment of nivolumab/ipilimumab-related infusion reactions.

DRESS, Drug Reaction with Eosinophilia and Systemic Symptoms; SJS, Suspected Stevens-Johnson syndrome; TEN, Toxic Epidermal Necrolysis

CONFIDENTIAL

Protocol XL184-313 Protocol Amendment 3.0  
Page 108 of 193

#### **6.6.3.2.1 Dose Delay and Restart Criteria for Nivolumab and Ipilimumab**

Immuno-oncology agents, such as nivolumab and ipilimumab, are associated with AEs that differ in severity and duration from AEs caused by other therapeutic classes. Early recognition and management of AEs associated with immuno-oncology agents may mitigate severe toxicity.

Delayed doses of nivolumab and ipilimumab should be administered as soon as the subject meets criteria to resume treatment. If a dose has been delayed, the subject should not wait until the next scheduled dosing date.

In addition to criteria and guidelines in [Table 6-10](#), subjects may resume treatment with these study drugs when the drug-related AE(s) resolve to Grade  $\leq 1$  or baseline value, with the following exceptions:

- Systemic corticosteroids for control of infusion reactions or irAEs must have been tapered to a dose level  $\leq 10$  mg/day of prednisone equivalent before resuming treatment with nivolumab/ipilimumab.
- If all study treatment is interrupted for  $> 12$  weeks, the subject must be permanently discontinued from study treatment unless approved by the Sponsor.

Refer to [Appendix E](#) for a complete list of criteria for resumption of nivolumab and ipilimumab treatment.

#### **6.6.3.2.2 Criteria for Discontinuation of Nivolumab and Ipilimumab**

If a subject meets criteria for discontinuation and the investigator is unable to determine whether the event is related to one or both checkpoint inhibitors, the subject should discontinue both nivolumab and ipilimumab with the exception of certain cases of liver function test elevation (See [Section 6.6.1](#)).

Prior to re-initiating treatment in a participant with a dosing delay lasting  $> 12$  weeks, the Medical Monitor must be consulted. Tumor assessments should continue as per protocol even if dosing is delayed. Periodic study visits to assess safety and laboratory studies should also continue as clinically indicated during such dosing delays.

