## **6.6 Safety Considerations**

Subjects will be monitored for SAEs from the time of signing informed consent and for nonserious AEs from first dose of study treatment. Monitoring continues through 100 days for unrelated SAEs ([Table 8-1](#)) after the date of the decision to permanently discontinue all study treatment (defined as the later of the date of the decision to discontinue all study treatment or the date of the last dose of any study treatment). Longer monitoring periods are required for related SAEs and certain other events as described in [Section 8.3](#). Further details for follow-up and data collection requirements for AEs, SAEs, and AESIs are summarized in [Appendix H](#). Subjects will be instructed to notify their physician immediately for any occurring AE. Causality assessment of AEs should include at minimum confounding factors such as disease and concomitant medications. Adverse event severity will be graded by the Investigator according to CTCAE v5.

The following should be taken into consideration in decisions regarding management for treatment-related side effects: cabozantinib, nivolumab, and ipilimumab have class-specific safety profiles based on their mechanisms of action but may also cause AEs that overlap.

- Examples of VEGFR-TKI associated AEs caused by cabozantinib are hypertension and hand-foot syndrome.
- Examples of irAEs caused by nivolumab are pneumonitis, colitis, hepatitis, nephritis, skin reactions, encephalitis, and endocrinopathies.
- Examples of irAEs caused by ipilimumab are hepatitis, endocrinopathies and hypophysitis.
- Examples of overlapping AEs are diarrhea and elevations in liver function tests (transaminases, bilirubin; see [Section 6.6.1](#)).

CONFIDENTIAL

Protocol XL184-313 Protocol Amendment 3.0  
Page 84 of 193

- As a general approach, all AEs should be managed with supportive care including both pharmacological and non-pharmacological treatments according to consensus management guidelines at the earliest signs of toxicity considered related to study treatment.
- Study treatment may be continued for mild AEs if appropriate supportive care has been initiated to ameliorate symptoms. Should this be ineffective and toxicities become unacceptable, dose modifications of study treatment should be considered to prevent worsening of toxicity. Moderate to severe AEs usually require dose modifications including dose reductions and/or interruptions.

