## GI Adverse Event Management Algorithm

Rule out non-inflammatory causes. If non-inflammatory cause is identified, treat accordingly and continue I-O therapy.  
Opiates/narcotics may mask symptoms of perforation. Infliximab should not be used in cases of perforation or sepsis.

[figure not shown]
Patients on IV steroids may be switched to an equivalent dose of oral corticosteroids (eg, prednisone) at start of tapering or earlier, after sustained clinical improvement is observed. Lower bioavailability of oral corticosteroids should be taken into account when switching to the equivalent dose of oral corticosteroids.

\* Discontinue for Grade 4 diarrhea or colitis. For Grade 3 diarrhea or colitis, 1) Nivolumab monotherapy: Nivolumab can be delayed. 2) Nivolumab+ Ipilimumab combination: Ipilimumab should be discontinued while nivolumab can be delayed. Nivolumab monotherapy can be resumed when symptoms improve to Grade 1. Please refer to protocol for dose delay and discontinue criteria for other combinations.

CONFIDENTIAL

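### For Grade 3 diarrhea or colitis with unclear attribution between the two checkpoint inhibitors, the protocol gives opposite instructions on nivolumab and does not say which prevails

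*Protocol*

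**What the plan says.** Three places in the protocol bear on the same event.

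- **Section 6.6.3.2.2** sets a general rule for a subject who meets a discontinuation criterion. Where the responsible antibody is uncertain, it reads: "unable to determine whether the event is related to one or both checkpoint inhibitors, the subject should discontinue both nivolumab and ipilimumab". It carves out one exemption: "with the exception of certain cases of liver function test elevation".
- **Table 6-10**, Colitis or Diarrhea, Grade 3, has a separate line for subjects on the combination: "When administered with ipilimumab: Permanently discontinue Ipilimumab". For the other antibody the row states "Nivolumab monotherapy may be resumed when AE resolves to baseline". Nivolumab is stopped for good only on recurrence: "If Grade 3 diarrhea or colitis recurs while on nivolumab monotherapy, permanently discontinue".
- **Appendix E**, GI Adverse Event Management Algorithm, points the same way as the table in its footnote: "Ipilimumab should be discontinued while nivolumab can be delayed".

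Section 6.6.3.2 introduces 6.6.3.2.1 and 6.6.3.2.2 as additional criteria and guidance beside Table 6-10. It gives no order of precedence.

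**The concern.** A subject with Grade 3 diarrhea or colitis on the combination meets a criterion for permanently stopping ipilimumab. If the investigator cannot say whether one or both antibodies caused the event, Section 6.6.3.2.2 on its wording ends nivolumab as well. The table and the Appendix E footnote let nivolumab resume after a delay. The texts disagree on whether nivolumab continues at all, which is a different matter from the grade to which the event must first resolve.

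At stake is consistent handling of a serious toxicity across about 180 sites, and with it the subject's further exposure to nivolumab, which is part of the backbone in both arms. The choice also feeds these SAP summaries:

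- reason for discontinuing nivolumab (Section 5.2);
- nivolumab exposure (Section 6.5.3);
- TEAEs leading to discontinuation of nivolumab or of all components (Section 8.1 and Table 15);
- AESIs leading to discontinuation (Table 16).

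**Working it through.** The main check is a comparison of texts; the plan states no figure to reproduce.

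**Step 1: is the trigger of Section 6.6.3.2.2 met?** The trigger names no drug and no type of event. Permanent discontinuation of ipilimumab is a discontinuation criterion, so Grade 3 diarrhea or colitis on the combination can meet it. The exemption covers some liver test elevations and no GI event.

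**Step 2: when do the instructions diverge?**

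| Investigator's view of the two antibodies | Section 6.6.3.2.2 | Table 6-10 and Appendix E | Conflict |
|---|---|---|---|
| Related to ipilimumab alone | Clause not triggered | Ipilimumab stops, nivolumab may resume | No |
| Related to both, with confidence | Clause not triggered on its wording | Ipilimumab stops, nivolumab may resume | No |
| Cannot tell whether one or both | Both stop | Ipilimumab stops, nivolumab may resume | Yes |

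**Step 3: is the third line realistic?** The protocol links colitis to each antibody. Section 6.6 states "Examples of irAEs caused by nivolumab are pneumonitis, colitis" and further events. Section 1.4 reports Grade 3-4 colitis in 14% and 33% of the two ipilimumab monotherapy groups, at loading and maintenance doses other than those used here. Uncertainty between the two is therefore plausible. No section gives its frequency.

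**Step 4: how many subjects?** The only triplet rate in the protocol is related Grade 3 or 4 diarrhea in 10% of 29 subjects, about 3, plus one Grade 3 or 4 immune-related colitis. These cover all dose levels and tumor types and are not limited to the four combination doses. Taking 5-10% as an assumption for Grade 3 diarrhea or colitis during those doses:

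- 0.05 × 840 = 42
- 0.10 × 840 = 84

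The number in conflict is this count times the fraction with unclear attribution, which the documents do not supply. So 42-84 is a ceiling under the assumed rate.

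**Step 5: how much nivolumab per subject?** Flat doses start at Week 14 and repeat every 4 weeks, to at most 2 years from the start of treatment. The last scheduled dose inside that limit is Week 102:

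- maximum: (102 − 14)/4 + 1 = 23 doses.

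The protocol expects 12-18 months on study treatment on average, roughly 52 to 78 weeks:

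- through Week 50: (50 − 14)/4 + 1 = 10 doses;
- through Week 78: (78 − 14)/4 + 1 = 17 doses.

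So 23 is the maximum, and 10-17 matches the protocol's expected average duration.

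**The case against.** The strongest reply is that the texts can be read together. Most permanent-discontinuation rows of Table 6-10 name no drug, and Section 6.6.3.2.2 can be taken as filling that gap. The Grade 3 colitis or diarrhea row does name the drugs separately. On this reading it creates a discontinuation criterion for ipilimumab only, and nivolumab reaches one only on recurrence. Appendix E agrees with the row, and Section 6.6.3.2.1 refers to Appendix E for the full resumption criteria. Section 3.6.1 allows one component to continue while another stops and encourages discussion with the sponsor. Appendix E also provides for discussion with the Medical Monitor.

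This is a reasonable reading, and it may be what the sponsor intends. It does not settle the matter. The general rule names no drug in its trigger, lists its exemption explicitly and omits this row. The pointer to Appendix E is not a precedence clause. The general permission in Section 3.6.1 does not address uncertainty between the two antibodies. Part of the Appendix E GI algorithm is a figure not available here, so only its footnote could be compared.

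Three stronger conclusions that a reader might draw are not supported:

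- **That every Grade 3 event on the combination meets opposite instructions, or that attribution is usually impossible.** No passage says so. Protocol Section 8.1.1 and SAP Section 8.1 require relatedness to be judged for each drug.
- **That 42-84 subjects are affected.** See Step 4: the attribution fraction is missing, and half of the 840 receive no cabozantinib, whereas the 10% comes from triplet subjects.
- **That the experimental arm will meet the conflict more often because diarrhea is also a cabozantinib toxicity.** That overlap raises a question between cabozantinib and the antibodies. Section 6.6.3.2.2 concerns uncertainty between the two antibodies. Diarrhea attributed to oral treatment is handled under Table 6-6. An arm difference is conjecture.

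**Conclusion.** The inconsistency is real but narrow. It arises for Grade 3 diarrhea or colitis during combination dosing when the investigator cannot tell whether one or both checkpoint inhibitors are responsible. In that case Section 6.6.3.2.2 ends nivolumab, Table 6-10 and the Appendix E footnote let it resume, and nothing says which prevails.

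The number of subjects cannot be derived from the documents. For a given subject, up to 23 scheduled flat doses depend on which text the site follows.

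The statistical reach is limited. The affected SAP outputs are descriptive, and SAP Section 8 plans no formal comparison of safety between arms. Tumor assessments continue whatever happens to treatment, and the PFS and OS estimands apply irrespective of whether the assigned treatment was given. Sample size, power and type I error are untouched. The case for acting rests on patient safety, consistent site practice and interpretable discontinuation and exposure tables.

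**What to change.** Reconcile Section 6.6.3.2.2, the Grade 3 colitis or diarrhea row of Table 6-10 and the Appendix E GI footnote, so that one stated rule governs nivolumab for this event when attribution between the antibodies is unclear. Editorially, either the general rule names this row as an exemption, or the row and footnote are changed to agree with the general rule. The sponsor's medical team decides which; this review takes no position. The same edit should state whether event-specific rows or Section 6.6.3.2.2 prevail where they differ.

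The cost is about one sentence in each affected place, by protocol amendment or site clarification memo, with no new data, visits or analyses.
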